		12.2.1 Physical Risks	
		12.2.2 Psychosocial and Privacy Risks	
4.0	BIOK	12.2.3 Adverse Event Reporting	
13	-		
14			
15		CEDURES AND INSTRUCTIONS	
	15.1	PROTOCOL AMENDMENTS	
	15.2	RECORDING OF DATA, DOCUMENTATION, AND RETENTION OF DOCUMENTS	
	15.3	PUBLICATION OF RESULTS	
	15.4	DISCLOSURE AND CONFIDENTIALITY	
16		CS AND GOOD CLINICAL PRACTICE	
	16.1	INSTITUTIONAL REVIEW BOARD/INDEPENDENT ETHICS COMMITTEE	
47	16.2	INFORMED CONSENT	
17	REFE	RENCES	16

Abbreviation	Term
AE	Adverse event
CABG	Coronary artery bypass grafting
CBC	Complete blood count
DASH	Disabilities of the Arm, Shoulder, and Hand Questionnaire
dRA	Distal radial artery
e-CRF	Electronic case report form
HIPAA	Health Insurance Portability and Accountability Act of 1996
ICH	International Council for Harmonisation
IRB	Institutional Review Board
PCI	Percutaneous coronary intervention
PHI	Protected health information
PI	Principal Investigator
pRA	Proximal radial artery
SAE	Serious adverse event

ABBREVIATIONS

SYNOPSIS	
Summary/Rationale:	This single-center, prospective, randomized study will evaluate distal radial artery (dRA) vs. proximal radial artery access (pRA) in regards to hand function and radial artery occlusion.
Study Objectives:	 Primary objective is to evaluate hand function following distal radial artery access compared to proximal artery access in patients undergoing cardiac catheterization. Hand function will be assessed by: QuickDASH questionnaire Hand grip test Thumb forefinger pinch test utilizing a pinch gauge Secondary objectives: Vascular access success rates, hematoma, bleeding, complications of vascular access and radial artery occlusion.
Study Design:	Single-center, prospective, randomized, study
Study Intervention(s):	Distal and proximal radial artery access
Number of Subjects:	300
Inclusion Criteria:	 A patient will be eligible for inclusion in this study if he or she meets all of the following criteria: 1. Age ≥ 18 years. 2. The distal and proximal radial artery must be palpable and non-occlusive flow must be confirmed by (Doppler) ultrasound. 3. Patient should be able to comply with the protocol. 4. Provide written informed consent before study participation.

SYNOPSIS

Exclusion Criteria:	 A patient will be ineligible for inclusion in this study if he or she meets any of the following criteria: Obligatory femoral or proximal radial access On therapeutic oral anticoagulation. Previous ipsilateral forearm radial artery occlusion. Very large hand/wrist anatomy that will preclude using the available hemostatic radial bands. Enrollment in another study that competes or interferes with this study. Poor clinical condition like cardiogenic shock, which prohibits pre- and post-procedural function tests. Subject with planned complex PCI or procedure necessitating multiple intervention. Any other condition or co-morbidity which, in the opinion of the investigator or operator, may pose a significant hazard to the subject if he or she is enrolled in the study. History of stroke with residual deficit that affects hand function Previous radial artery catheterization within 1 year. 	
Sponsor:	Baylor Scott and White Research Institute	
Principal Investigator:	[name]	
Primary Study Site/Data Center:	The Heart Hospital Baylor Plano [name]	
Duration of Study:	2 years	

5. STUDY OBJECTIVES

The primary objective of this study is to evaluate hand function following distal radial artery access compared to proximal artery access in patients undergoing cardiac catheterization.

Hand function will be assessed by:

- QuickDASH questionnaire
- Hand grip test
- Thumb forefinger pinch test utilizing a pinch gauge

Secondary endpoints include success rates, hematoma, bleeding, rates of radial artery occlusion and complications of vascular access.

6. STUDY DESIGN

This is a prospective, randomized, single-center clinical trial.

This study will assess the outcomes of hand function utilizing the QuickDASH questionnaire, hand strength using the hand grip test, and the thumb and forefinger pinch using an electronic pinch gauge. Rates of radial artery occlusion in patients undergoing cardiac catheterization using dRA compared to pRA will be analyzed using ultrasound doppler at 1 month and 1 year.

Approximately 300 patients undergoing coronary angiography or angioplasty at The Heart Hospital Baylor Plano will be randomized 1:1 to distal or proximal radial access for cardiac catheterization.

7. ASSESSMENT OF HAND FUNCTION

Hand function will be assessed by the following:

1. QuickDASH questionnaire

The DASH outcome measurement is used around the world by clinicians and researchers as a tool for self-reported outcome concerning upper-limb musculoskeletal disorders (Hudak P). It consists of two components: symptom questions of 30 items with scores from 1 to 5, and optional high performance (sport/music or work) section of 4 items also with scores of 1 to 5.

The optional modules which concern sport, music or work are not used as those are mainly utilized to identify the specific limitations by professional athletes and performing artists or other group of workers.

This study will be using the abbreviated, QuickDASH questionnaire. The purpose of the QuickDASH is to use 11 items to measure physical function and symptoms. It decreases responder and data entry burden while maintaining a high degree of correlation to the original length DASH.

2. *Pinch grip by use of a pinch grip dynamometer*. Baseline® Mechanical Pinch Gauge (Baseline Medical, Quakertown, PA, USA) will be used to measure pinch force between thumb and forefinger. This device is CE certified and is commonly used by physiotherapists. It is utilized to evaluate tendon or nerve injury and neuromuscular disorders. Pinch strength will be recorded in kilograms.

3. Hand Grip Test (using a Jamar Hand Hydraulic dynamometer)

18. STUDY POPULATION

The study population will consist of adult male and female patients undergoing cardiac catheterization at The Heart Hospital Baylor Plano.

8.1 Eligibility Criteria

8.1.1 Inclusion Criteria

A patient will be eligible for inclusion in this study if **he or she** meets **all** of the following criteria:

1. Age \geq 18 years.

2) The distal and proximal radial artery must be palpable and non-occlusive flow must be confirmed by (Doppler) ultrasound.

3) Patient should be able to comply with the protocol.

4) Provide written informed consent before study participation.

8.1.2 Exclusion Criteria

A patient will be ineligible for inclusion in this study if **he or she** meets **any** of the following criteria:

- 1) Obligatory femoral or forearm radial access
- 2) Previous ipsilateral forearm radial artery occlusion.
- 3) Patient on therapeutic oral anticoagulation.
- 4) Very large hand/wrist anatomy that will preclude using the available hemostatic radial bands.
- 5) Enrolment in another study that competes or interferes with this study.

- 6) Poor clinical condition like cardiogenic shock, which prohibits pre- and post-procedural function tests.
- 7) Subject with planned complex PCI or procedure necessitating multiple intervention.
- 8) Any other condition or co-morbidity which, in the opinion of the investigator or operator, may pose a significant hazard to the subject if he or she is enrolled in the study.
- 9) History of stroke with residual deficit that affects hand function.
- 10) Previous radial artery catheterization within 1 year.

9. STUDY VISITS AND ACTIVITIES

9.1 Screening and Baseline

Subjects must meet the inclusion criteria and have none of the exclusion criteria in order to be eligible for participation in this study.

Screening assessments will be collected through review of medical records and by interview after informed consent is signed. These screening evaluations may include:

- Complete Medical History (including history of myocardial infarction, diabetes mellitus, hypertension, hypercholesterolemia, previous CABG and PCI)
- Demographics
- Vital Signs (Including height and weight)
- Physical Exam
- Labs
 - Complete Blood Count (CBC) including platelet count
 - Basic metabolic panel
 - o INR, PTT if available, not mandated

Women of child-bearing potential will also receive a pregnancy test.

If measurement of any of the above assessments does not occur in the normal course of patient care, clinical practice should not be changed to accommodate collection of additional data.

A mandatory screening assessment for research purposes will include, assessing the patency of the proximal and distal radial artery with Doppler ultrasound.

Pre-Procedure Baseline evaluations will include:

- 1. Assessment of hand function (bilaterally)
 - Completion of the QuickDASH questionnaire
 - Assessment of the hand grip strength using the hand dynamometer.
 - Assessment of pinch grip by use of a pinch grip dynamometer. Baseline® Mechanical Pinch Gauge

9.2 Enrollment

The lead statistician will use a random number generator to produce a randomization scheme that will be used by the study coordinator(s) to allocate study participants to distal or proximal access study arms after informed consent is obtained, all inclusion/exclusion is assessed, and the participant is found to be eligible for the study.

Participants randomized to proximal access will receive conventional access procedure according to standard of care.

9.3 Distal Radial Access Procedure

Participants randomized to distal radial access will have the procedure as follows (Kiemeneij). Patients will receive appropriate peri-procedural antiplatelet and anticoagulation medications according to standard hospital practice.

The left or the right upper arm is placed comfortably on a cushion on the ipsilateral side of the patient. The hand is placed in a mid-supination position. For right distal radial access, the right wrist rests on a comfortable underground which brings the wrist in passive ulnar flexion. The patient is asked to bring the thumb under the other four fingers. This brings the artery more to the surface which allows easier puncture. After disinfection, the patient is covered with a sterile drape. A brachial drape is applied to the hand exposing the anatomical snuff box and the proximal radial.

Under ultrasound guidance, local anesthesia is applied by subcutaneous injection of 5cc of lidocaine filling the radial fossa. The puncture will be performed at the point of maximal pulsation proximal in the anatomical snuffbox. If this fails, a puncture more distal, just outside the snuffbox can be attempted. The puncture is preferably done with the traditional radial needle. After successful anterior wall puncture a radial sheath wire is advanced. Proper position is verified by fluoroscopy or by ultrasound to ensure the wire didn't traverse the palmar arch. This is followed by introduction of a hydrophilic sheath. The size of the sheath used will be documented (5 or 6 french radial sheaths). In order to prevent damage to the tip of the introducer and sheath, which might damage the artery, a small skin incision can be made followed by introducing the sheath. After administration of a spasmolytic cocktail containing 200-400 mcg of nitroglycerin and 5 mg of verapamil, the operator can take up a position at the level of the patient's knees. The choice of wire is at discretion of the operator. In case of left sided access, usually the wire encounters some resistance at the flexed left elbow. Careful manipulation of the wire direction with the tip of the catheter will usually solve the problem. If necessary a hydrophilic wire under fluoroscopy, can be used with special attention not entering small side branches in order to prevent perforation.

Hemostasis is performed using a radial hemostatic band, but with the least possible pressure and the shortest possible time (patent hemostasis). Technique, device used, and time will be recorded in the electronic case report form (e-CRF). Following the procedure, the patient is free to use both arms. No special supportive slings or other mobility limitation measures are required.

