9.4 Follow-up

Subject management post-procedure will proceed via standard institutional protocol. Subjects will have a follow-up visit one month and 12 months post-procedure (\pm 10 days).

Follow-up visit assessments at 1 month and 12 months will include:

- 1. Any clinical change, reinterventions using the radial artery between the index procedure and follow up, is to be recorded.
- 2. Assess patency of the proximal and distal radial artery with Doppler ultrasound.
- 3. Assessment of hand function
 - Completion of the QuickDASH questionnaire
 - Assessment of the hand grip, using the hand dynamometer.
 - Assessment of pinch grip by use of a pinch grip dynamometer. Baseline® Mechanical Pinch Gauge

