14.1 Analysis of Primary Composite Outcome

The primary composite outcome of hand function will be defined utilizing the average Z-score approach (O'Brien, 1984; Sun, 2012). The average z-score for each subject is calculated as the average of the z-scores of the differences between pre- and 1-month post-operation measurements for three individual tests. The three tests that measure everyday functionality and strength of a subject's hand included in the composite outcome are: (a) the QuickDASH questionnaire score (0-100) calculated as [(sum of n responses / n) – 1] * 25, (b) Thumb and forefinger pinch strength test (kg), and (c) hand grip strength test (kg). The average of the three z-scores are then compared between rDA and pDA using the Wilcoxon rank-sum test.

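### Does leaving the tested hand, the access side and hand dominance unstated undermine the hand-function result?

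*Combined protocol and SAP*

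**What the plan says.** Only distal versus proximal access is randomised. In the distal arm either side may be used: "The left or the right upper arm is placed comfortably on a cushion on the ipsilateral side of the patient" (section 9.3). In the proximal arm no side is given: "Participants randomized to proximal access will receive conventional access procedure according to standard of care" (section 9.2). One exclusion criterion is "Previous ipsilateral forearm radial artery occlusion" (section 8.1.2), which presupposes an intended side when eligibility is judged.

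Before the procedure the plan calls for "Assessment of hand function (bilaterally" (section 9.1). At 1 and 12 months the list reads, for example, "Assessment of the hand grip, using the hand dynamometer" (section 9.4), with no hand named. The same visits record "reinterventions using the radial artery between the index procedure and follow up".

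The primary outcome averages the z-scores of "the differences between pre- and 1-month post-operation measurements for three individual tests" (section 14.1): QuickDASH, pinch and grip. Section 14.1 speaks of the subject's hand in the singular and does not say accessed, dominant or mean of both. The test is stated plainly: "The average of the three z-scores are then compared between rDA and pDA using the Wilcoxon rank-sum test".

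The procedure items named for recording in section 9.3 are sheath size and the technique, device and time of hemostasis. Side is not among them, and hand dominance is not mentioned anywhere.

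**The concern.** Two of the three components of the primary outcome, grip and pinch, are measured one hand at a time. Section 4.1 worries about local injury, because the distal artery runs close to the radial nerve. A reading from the hand that was not punctured cannot show such injury. If those readings entered the composite, they would pull the comparison towards no difference, and that would be taken as reassurance about distal access.

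The second worry is side. If operators chose the side knowing the arm, the left/right mix could differ between arms. Without side and handedness on record, nobody could then tell an effect of the puncture site from an effect of which hand was used.

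**Working it through.** **1. The plan's own figures.** Section 14.4 gives 125 evaluable per group, correlation 0.3, at least 80% power and 15% loss. 125/0.85 = 147.1, so 148 per arm and 296 in total, as stated.

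For power I read the 10% ± 10% change as a 1 SD shift in one test. I assume a two-sided 5% level, which section 14 does not state, and three change scores scored in the same direction. With the shift on grip and the accessed hand analysed:

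- pooled SD of grip = √(1 + 1²/4) = 1.118
- difference in mean z = (1/1.118)/3 = 0.298
- SD of the average z = √[(2 + 1/1.118² + 2×0.3 + 4×0.3/1.118)/9] = 0.705
- standardised difference = 0.298/0.705 = 0.423
- Wilcoxon noncentrality = 0.423 × √[(125/2)(3/π)] = 0.423 × 7.73 = 3.27
- power = Φ(3.27 − 1.96) = 90%

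Simulation gives about 91%. Both agree with the plan's claim of at least 80%.

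**2. What wrong-hand readings would cost.** Let a share p of distal-arm grip and pinch readings come from the unpunctured hand. For a grip-only effect at p = 30%, the distal mean is 0.7 and its variance 1 + 0.3×0.7 = 1.21. The pooled SD is √[(1 + 1.21)/2 + 0.7²/4] = 1.108 and the difference in mean z is 0.7/1.108/3 = 0.211. The SD of the average z is 0.714, the noncentrality 2.28 and the power 63%. Simulated power for each placement of the effect that section 14.4 allows (at least one of the three tests):

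| 1 SD effect on | p = 0 | 10% | 30% | 50% |
|---|---|---|---|---|
| grip only | 91% | 84% | 63% | 37% |
| QuickDASH only | 91% | 91% | 91% | 91% |
| grip and pinch | 100% | 100% | 99.7% | about 90% |
| all three | 100% | 100% | 100% | 100% |

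The result runs from no loss to a large loss, and every value of p is an assumption.

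**3. What averaging both hands would cost.** The effect on a strength test is halved and its SD shrinks by √((1 + r)/2), where r is the between-hand correlation of change. A 1 SD effect becomes 0.5/√((1 + r)/2) = 0.62, 0.58 or 0.54 SD at r = 0.3, 0.5 or 0.7. For grip only, power is about 53%, 49% or 45%. If grip and pinch both carry 1 SD and r = 0.5, each shift is 0.577 SD. The pooled SD is √(1 + 0.577²/4) = 1.041, the difference in mean z is 2×0.577/1.041/3 = 0.370, the SD of the average z is 0.711, and the noncentrality is 0.520 × 7.73 = 4.02. Power is 98%.

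**4. Which reading the text supports.** Section 5 sets the aim as hand function following access, and section 14.1 takes a pre-to-post difference in one hand. Testing both hands beforehand guarantees a baseline for whichever hand is later punctured. By follow-up the accessed side is known. Section 9.4 also asks for radial patency without naming a side, and asks about reinterventions through the radial artery, so the visit already presumes that the index artery is known. Whether follow-up tests both hands or only the accessed one, the accessed hand's change can be computed.

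**5. Side.** Take a pure puncture-site effect as the target, and suppose QuickDASH alone shifts by 0.2 to 0.4 SD with dominance. The noncentrality is imbalance × shift × 0.456 × 7.73, where 0.456 = (1/3)/√((3 + 6×0.3)/9). Rejection is 5.1–5.2% at a 10-point side imbalance and 6.4–10.9% at 50 points. The documents show no imbalance at all.

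**The case for a change.** The strongest case for acting is that a primary endpoint should not rest on inference. Baseline names both hands, so an analyst could average them without making any error, and for an effect on grip alone that would cost about 38 to 46 points of power (91 − 53 to 91 − 45). Two analysts could obtain different primary results from the same data. A second-hand reading not taken at 1 month is lost, as is the side the operator intended before allocation.

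Some of this stands. The text is silent, the averaging arithmetic is right, and those two items cannot be recovered reliably. They do not carry the conclusion, for three reasons. The large losses need an effect confined to one strength test together with a choice of hand that defeats the stated aim. The second-hand reading is not needed for the accessed-hand comparison; it would serve only an internal-control analysis that the plan does not make. Intended side matters only for separating puncture site from side, whereas section 5 asks about distal against proximal access. Under that question the side chosen is part of the access as delivered, and randomisation protects the comparison.

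Nor is it established that side could never be examined. Section 15.2 requires source documents for each subject, from which the side used is likely to be recoverable. Handedness is stable and can be asked at either follow-up visit. The case report form is not among the documents, so silence in the protocol does not show that these items are uncollected.

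**Conclusion.** The observation about the text is correct: the hand is not named in sections 9.4 and 14.1, access side is not listed for recording, and dominance is absent. It is a gap that staff and analysts would fill sensibly with the accessed hand, and no stated rule has been shown to give a wrong result. On that reading power is about 91% for a 1 SD shift in one test, and 125 evaluable (148 enrolled) per arm stands.

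The possible cost of another reading runs from zero to a fall to 37%. It depends on where the effect lies and on wrong-hand shares that the documents do not supply, so the low figures are a least-favourable case. The side question is weaker still: no imbalance is shown, the shift with dominance is assumed, and the comparison of access strategies remains valid. The conclusion rests on the accessed hand being tested at 1 month, which sections 5, 9.1 and 14.1 together support. No change to the plan follows.

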9.4 Follow-up

Subject management post-procedure will proceed via standard institutional protocol. Subjects will have a follow-up visit one month and 12 months post-procedure (\pm 10 days).

Follow-up visit assessments at 1 month and 12 months will include:

- 1. Any clinical change, reinterventions using the radial artery between the index procedure and follow up, is to be recorded.
- 2. Assess patency of the proximal and distal radial artery with Doppler ultrasound.
- 3. Assessment of hand function
 - Completion of the QuickDASH questionnaire
 - Assessment of the hand grip, using the hand dynamometer.
 - Assessment of pinch grip by use of a pinch grip dynamometer. Baseline® Mechanical Pinch Gauge

9.5 Withdrawal from Study

Subjects may voluntarily discontinue participation in the study at any time, for any reason. The Investigator also has the right to discontinue subjects from the study if he/she feels it is in the best interest of the subject.

10. COMPENSATION

Participants will not receive any compensation for participating in this study.

11. COSTS

Participants will not incur any additional research-related costs due to study participation. Subject or their insurance company will be required to pay for all expenses related to regular care including procedure and other hospital care.

12. RISK AND BENEFITS TO PARTICIPANTS

12.1. Potential Benefits

There is no guarantee of direct benefit to the subjects who participate in this study. There is a possibility that dRA will reduce the risk of bleeding and radial artery occlusion as well as improve patient comfort. Future patients may benefit from the knowledge gained.

12.2. Potential Risks

12.2.1 Physical Risks

Possible risks include loss of sensory function in part of the hand if the cutaneous nerve running in the anatomical snuffbox becomes damaged, distal embolization can result in digital ischemia and occlusion of the branch supplying the scaphoid bone can result in bone necrosis.

A study with 656 patients reported an incidence of distal radial artery occlusion of 1.5%, haematoma of wrist and forearm (0,8%), edema (0.2%), numbress (0.6%), dissection (0.3%), arteriovenous fistula (0.2%), transient ischemic attack (0.2%), stroke (0.2%), aneurysm (0.2%), death (0.5%) (Kaledin AL, 2014;27).

A skilled and experienced operator minimizes such complications. Operators with adequate experience in distal radial access at the discretion of the Principal Investigator are eligible to participate.

